8.5 Non-Relapse Mortality (NRM)

Non-relapse mortality (NRM) rates will be calculated using a cumulative incidence estimate for visual purposes. NRM will be defined as the occurrence of death without prior relapse, with relapse a competing risk for NRM. For each subject, time to death will be calculated as described in the above OS section and time to relapse will be calculated as described in the DFS section.

Event and censoring assignments will proceed as follows:

- Subjects with no relapse and no death will be censored at the last time known to be alive.
- Subjects with no relapse who die will be counted as events.
- Subjects with relapse will be considered a competing risk at the time of first relapse.
- Follow-up will not extend beyond one year.

8.6 Acute GVHD-Free Survival (GFS)

Failure for the composite endpoint Grades II-IV aGvHD-free survival at Day 180 is the occurrence of Grades II-IV aGvHD by Day 180 or death. The time of failure, if both components occur, is the earliest of the two failures; if only one component occurs time of failure is the day of that failure. Grades III-IV aGvHD-free survival at Day 180 will also be calculated. For each of these, aGvHD will be graded according to Keystone criteria. Kaplan-Meier estimates of each will be provided for visual purposes, and in addition to the point estimates at Day 180, point estimates at one year will also be provided. Censoring is performed as described in the Acute GVHD and Overall Survival sections above. There are no competing risk events.

8.7 GvHD-Free, Relapse-Free Survival (GRFS)

GRFS rates will be calculated using Kaplan-Meier methodology. For each subject, GRFS will be calculated as time from first infusion of RGI-2001 to date of Grade III-IV aGVHD (defined below), moderate-to-severe cGVHD requiring systemic immune suppression (defined below), disease relapse or progression (defined above), or death by any cause (using *Discontinuation* eCRF), whichever occurs first. Censoring: Subjects who do not experience any of these events will

be censored on the last evaluation of relapse/progression (3 dates from last *Disease Status* eCRF), with follow-up truncated at one year (365 days). There are no competing risk events.

Date of first Grade III-IV aGvHD will be obtained using Keystone Grading and the diagnosis date recorded on the *aGvHD_d* eCRF.

Date of first use of systemic therapy for cGvHD will be defined using the *Concomitant Medication* eCRF as described in “Time to First Use of Systemic Therapy for GvHD” section below.

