**5 STUDY OBJECTIVES AND ENDPOINTS**

Objectives	Endpoints
Primary	

 
To assess the potential efficacy of RGI-2001 in addition to standard of care (SOC) vs SOC for the prevention of aGvHD
 
To characterize the safety and tolerability of 6-weekly IV infusions of RGI-2001 in subjects following alloHSCT
 
	
 
Efficacy: Grades II-IV aGvHD by Day 100 according to the Modified Keystone Criteria (Przepiorka 1995)
 
Safety: Incidence, nature, and severity of treatment-emergent AEs, SAEs, laboratory test values, vital sign measures, and graft failure
 

Secondary	

 
To assess the potential efficacy of RGI-2001 in addition to SOC vs SOC for the prevention of chronic GvHD (cGvHD) according to the secondary endpoints listed
 
To assess the survival of subjects who received RGI-2001 in addition to SOC vs SOC
 
To evaluate the pharmacodynamics effects of weekly dosing of RGI-2001
 
	
 
Grades II-IV aGvHD by Day 180 according to the Modified Keystone Criteria
 
Total and moderate-severe cGvHD at 6 months and 1 year according to 2014 NIH criteria
 
Non-relapse mortality (NRM) rates at Day 100, 6 months and 1 year
 
Disease-free survival (DFS) at 6 months and 1 year
 
GvHD-free, relapse free survival (GRFS)a at 6 months and 1 year
 
Overall survival (OS) at 6 months and 1 year
 
Change from baseline in the percentage of CD4+CD25+CD45RA+ CD127-LO T cells (naive Tregs) on Days 14, 28, 42, 60, 100, 180
 

 
[REDACTED]
 
	
 
[REDACTED]
 

Objectives	Endpoints
	

• [REDACTED]

• [REDACTED]

a A GRFS event includes grade III-IV acute GVHD, chronic GvHD requiring systemic immunosuppressive treatment, disease relapse or progression, or death by any cause.

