**NIH Global Severity of Chronic GvHD**

Mild chronic GvHD	1 or 2 organs involved with no more than score 1 plus Lung score 0
Moderate chronic GvHD	3 or more organs involved with no more than score 1 OR At least 1 organ (not lung) with a score of 2 OR Lung score 1
Severe chronic GvHD	At least 1 organ with a score of 3 OR Lung score of 2 or 3
Key points:	In skin: higher of the two scores are to be used for calculating global severity. In lung: FEV1 is used instead of clinical score for calculating global severity. If the entire abnormality in an organ is noted to be unequivocally explained by a non-GvHD documented cause, that organ is not included for calculation of the global severity. In the abnormality in an organ is attributed to multifactorial causes (GvHD plus other causes) the scored organ will be used for calculation of the global severity regardless of the contributing causes (no downgrading of organ severity score).

Source: Jagasia, Madan H. et al. National Institutes of Health Consensus Development Project on Criteria for Clinical Trials in Chronic Graft-versus-Host Disease: I. The 2014 Diagnosis and Staging Working Group Report. *Biology of Blood and Marrow Transplantation*, 2015 March; 21 (3):389–401

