8.0 EVALUATION OF EFFICACY PARAMETERS

All efficacy analyses will be performed on the Safety Analysis Population. As noted above, outcomes will ultimately be compared to data obtained from the CIBMTR and details of this comparison are contained in a separate SAP that is specific to this goal. Methods for estimation of efficacy parameters are provided below without mention of the methods that will be used for comparing efficacy parameters to the CIBMTR data.

Binary outcomes will be summarized with proportions, continuous outcomes with means and medians, and time-to-event outcomes with Kaplan-Meier estimates or cumulative incidence estimates for endpoints with competing risks.

Definitions of occurrence and timing of outcomes are described below.

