8.2 Chronic GvHD

Chronic GvHD (cGvHD) will be summarized visually as a function of time up to one year as a cumulative incidence estimates as well as by-visit frequency analysis.

Severity ratings according to 2014 NIH Criteria will be used. Event time will be defined as the time from the “start date” of first RGI-2001 infusion (i.e., transplant date) to the first date cGvHD is diagnosed with moderate or severe cGvHD (if multiple cGvHD_d eCRFs exist with moderate/severe ratings, the first diagnosis date across the eCRFs will be used for this event). Censoring: Subjects who are alive without these events will be censored at the date of completion of the last cGvHD assessment, with follow-up truncated at one year (365 days). Subjects who die or relapse without cGVHD will be treated as competing-risk events at the time of death. The occurrence of cGVHD as a function of time will be calculated using cumulative-incidence estimates.

Similar to above, the analysis will be repeated for using all severities (not just moderate and severe).

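### SAP 8.7 narrows the chronic GvHD part of GRFS relative to the protocol, and SAP 8.2 dates relapse at death; two smaller points in 8.7 and 8.5 need settling

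*SAP*

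**What the plan says.** **GRFS.** Protocol Section 5, footnote a, lists grade III-IV acute GvHD together with "chronic GvHD requiring systemic immunosuppressive treatment, disease relapse or progression, or death by any cause". SAP 8.7 instead requires "moderate-to-severe cGVHD requiring systemic immune suppression (defined below"). What follows in 8.7 is a date rule only: "Date of first use of systemic therapy for cGvHD will be defined using the" concomitant medication form, as described in 8.8. Neither 8.7 nor the visible text of 8.8 contains a severity step. Protocol Appendix 4 recognises mild chronic GvHD: "1 or 2 organs involved with no more than score 1", with lung score 0.

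**Chronic GvHD.** SAP 8.2 states: "Subjects who die or relapse without cGVHD will be treated as competing-risk events at the time of death". It also states: "Subjects who are alive without these events will be censored at the date of completion of the last cGvHD assessment". For NRM, SAP 8.5 dates relapse differently: "Subjects with relapse will be considered a competing risk at the time of first relapse". SAP 8.4 defines that relapse date.

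**Acute GvHD within GRFS.** SAP 8.1 takes the first diagnosis date across *aGvHD_d* (initial report) and *aGvHDmax* (maximum report), and repeats the analysis for grades III-IV. SAP 8.7 names *aGvHD_d* only.

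**Progression.** SAP 8.4 codes and dates progression separately from relapse and counts both as DFS failures. SAP 8.5 mentions relapse only.

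**Scope.** On the comparison with CIBMTR controls, SAP 8.0 says that "details of this comparison are contained in a separate SAP that is specific to this goal".

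**The concern.** GRFS, chronic GvHD and NRM are named secondary endpoints in both documents. If the SAP's GRFS event is narrower than the protocol's, the reported GRFS rate does not estimate the endpoint the protocol defines. On a crude rate the restriction can only raise GRFS or leave it unchanged.

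The 8.2 rule raises a different problem: it cannot be carried out for every subject. A relapsed subject alive at one year has no death date, yet is called a competing event and also fits the rule for living, event-free subjects. Two programmers could treat that subject differently and both claim to follow the SAP.

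The form used in 8.7 and the silence on progression in 8.5 raise the same kind of doubt on a smaller scale.

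**Working it through.** The documents give no figure to reproduce. The check compares definitions and then gauges size.

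**1. GRFS component.** How each text classifies a subject on systemic treatment for chronic GvHD:

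| Severity | Protocol Section 5, footnote a | SAP 8.7 wording |
|---|---|---|
| Mild | event | not an event |
| Moderate or severe | event | event |

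The texts differ in the first row. SAP 2.3 plans 50 treated subjects, so each subject whose only GRFS event falls in that row moves the crude rate by 1/50 = 2 points. For scale, the standard error of a 50% rate is sqrt(0.25/50) = 7.07 points, so one subject is 2/7.07 = 0.28 standard errors. The documents give no basis for the number of such subjects.

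**2. Competing-event date in 8.2.** How each type of subject without chronic GvHD is handled:

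| Subject | 8.2 competing rule | 8.2 censoring rule |
|---|---|---|
| Dies, no relapse | at death | does not apply |
| Relapses, then dies | at death, later than relapse | does not apply |
| Relapses, alive at day 365 | named as competing, no date | also applies |
| Alive, no relapse | does not apply | applies |

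The third row is where the rule fails.

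To gauge size I assumed one-year cumulative incidences of 30% chronic GvHD, 10% death without relapse, and 10, 20 or 30% relapse, each as a first event, with 60% mortality in the year after relapse. All are assumptions. With constant hazards and time in years:

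- Total hazard L = −ln(1 − sum of the three incidences). Each cause takes its share of L. At 20% relapse, L = −ln(0.40) = 0.916; the hazards are 0.458 (chronic GvHD), 0.305 (relapse) and 0.153 (death).
- Post-relapse death hazard d = −ln(0.40) = 0.916.
- If chronic GvHD after relapse is counted at hazard h, the added incidence is the integral over u from 0 to 1 of (relapse hazard) × exp(−Lu) × [h/(h + d)] × [1 − exp(−(h + d)(1 − u))].
- Relapsed survivors are the integral of (relapse hazard) × exp(−Lu) × exp(−d(1 − u)). At 20% relapse L = d, so this is 0.305 × 0.40 = 0.122, or 6.1 of 50.

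| One-year chronic GvHD incidence | Relapse 10% | 20% | 30% |
|---|---|---|---|
| Dated at earlier of relapse or death | 30.0% | 30.0% | 30.0% |
| Dated at death, none counted after relapse, full follow-up | 30.0% | 30.0% | 30.0% |
| Dated at death, counted after relapse at half the earlier hazard | 30.8% | 31.8% | 33.1% |
| Same, at the full earlier hazard | 31.5% | 33.4% | 35.8% |
| Relapsed survivors censored at relapse, none counted after relapse | 31.0% | 32.1% | 33.4% |
| Relapsed survivors with no defined date, of 50 | 3.1 | 6.1 | 9.0 |

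The second row shows no shift because, without censoring, the estimate is simply the proportion with chronic GvHD by day 365, whatever date the competing event carries. The shift comes either from counting chronic GvHD after relapse or from censoring relapsed survivors early. The range is 0 to 35.8 − 30.0 = 5.8 points.

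A second set of assumptions gives a similar picture. With net one-year risks of 40% chronic GvHD, 12% death without relapse, 15/25/35% relapse and the same post-relapse mortality, dating at relapse gives 35.2/33.3/31.4%. Counting chronic GvHD after relapse at the same hazard gives 37.3/36.9/36.4%, and censoring survivors at relapse gives 36.6/35.6/34.5%. The shifts run from 36.6 − 35.2 = 1.4 to 36.4 − 31.4 = 5.0 points.

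**3. Acute GvHD source.** A subject first reported below grade III who later worsens enters the 8.1 grade III-IV analysis through either form. Under 8.7 that subject is captured, and correctly dated, only if *aGvHD_d* is filed again at worsening. The eCRF is not available to settle this. If the event is missed, Tables 14.2.2.1 (acute GvHD) and 14.2.2.7 (GRFS) would disagree about the same subject.

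**4. Progression.** Read literally, a death after coded progression without coded relapse is NRM under 8.5, although 8.4 counts the progression as disease failure. Section 8.5 takes its time to relapse from the DFS section, so progression may be meant.

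**The case against.** **On GRFS.** The only operational rule in 8.7 is the therapy start date. A program built on it might apply no severity filter and so match the protocol. The SAP cites protocol Version 2.0, while the version of the protocol reviewed cannot be seen; nor can the text of the SAP 1.1 footnote attached to GRFS. These limits stand. They make the SAP unclear, but they do not remove a restriction that 8.7 states outright.

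**On 8.2.** Acute GvHD in 8.1 has death as its only competing event. On that model the slip is the mention of relapse, death is the right date, and chronic GvHD after relapse is part of the quantity wanted, not bias. That reading is coherent, and the visible protocol does not rule it out. Either way the present sentence fails for relapsed survivors.

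**On the acute GvHD source.** Section 8.1 refers to *aGvHD_d* forms in the plural, and 8.2 shows that the chronic counterpart can repeat. A reader might infer that 8.7 will lose worsening cases. The documents do not establish that; they show only a narrower source for the same event.

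**On NRM.** A reader might call 8.5 and 8.4 contradictory. They are not: NRM and DFS may have different components, and the visible protocol gives no NRM event definition.

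**Conclusion.** Two corrections are warranted: the severity limit in 8.7, which departs from the protocol text reviewed, and the relapse date in 8.2, which cannot be applied as written. The acute GvHD source in 8.7 is a real difference from 8.1 whose effect depends on the eCRF. Progression in 8.5 is a request for clarification.

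The size is 2 points per reclassified subject, number unknown, and 0 to about 6 points for chronic GvHD incidence under wholly assumed rates, depending mainly on whether chronic GvHD after relapse is counted.

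A reader might infer that these definitions tilt the comparison with controls towards RGI-2001. The documents do not support that. The comparison is governed by another SAP whose definitions cannot be checked, and the net direction across endpoints is unknown. The primary Day 100 acute GvHD endpoint is unaffected.

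**What to change.** - **SAP 8.7, chronic GvHD:** use the protocol's component, chronic GvHD requiring systemic immunosuppression at any severity.
- **SAP 8.2:** because it names relapse as competing, date the competing event at the earlier of first relapse (as defined in 8.4 and used in 8.5) or death. Censor only subjects alive without chronic GvHD and without relapse. If relapse is not meant to compete, as in 8.1, delete the mention of relapse instead and keep following relapsed subjects for chronic GvHD.
- **SAP 8.7, acute GvHD:** read grade III-IV from both *aGvHD_d* and *aGvHDmax*, keeping the 365-day follow-up already in 8.7. First check in the eCRF whether *aGvHD_d* is refiled at worsening and whether *aGvHDmax* holds the date on which grade III-IV was reached.
- **SAP 8.5:** state whether progression counts with relapse as the competing event for NRM.

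The cost is SAP wording, programming and the two eCRF checks. The CIBMTR SAP should be checked for the same definitions.

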8.8 Time to First Use of Systemic Therapy for GvHD

Date of first use of systemic therapy will be defined using the *Concomitant Medication* eCRF. A subset of the *Concomitant Medication* eCRFs will be used to identify the first start date for the medication; this subset is defined in the TLF attachment on the applicable table. This time analysis will be tabulated using continuous methods (mean/median/etc), and number of patients with at least one of these medications will be calculated using a simple proportion of the safety population.

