4.0 STATISTICAL METHODS OF ANALYSIS

4.1 Statistical Considerations

Continuous variables will be summarized (based on the subjects with non-missing values) by the number of subjects (n), mean, standard deviation (SD), median, minimum value, and maximum value. Mean and median will be accurate to one more digit decimal point than the original data, and standard deviation will be accurate to two more-digit decimal points than the original data, and the decimal points of the maximum and minimum values will be the same as the original data.

Categorical variables will be summarized (based on the subjects with non-missing values) by the frequency (count and percent) of subjects falling within the category. The denominator for all

percentages, unless otherwise specified, will be the number of subjects in the specified analysis population.

Point estimates of time-to-event outcomes will be obtained using either Kaplan-Meier or cumulative incidence estimates, depending on whether endpoints have competing risks. Survival at a variety of specific endpoints will be presented in the tabled output, including Day 100 (i.e., primary endpoint for aGvHD) and Day 365 (i.e., EOS). In addition (if applicable), the median length of survival (in days) will be presented. Furthermore, listed data for all time-to-event outcomes will be provided.

Regarding the time-to-event estimates, the time between begin and end dates for events and censors is important in the calculation. If either of the dates are invalid, then the 1st will be assumed (for missing day) and/or January will be assumed (for missing month). Assumptions will only be incorporated into the analysis if calculation of time does not result in a negative number of days. If negative, the subject will not be used in the analysis. If assumptions are needed, they will be flagged in the listings.

Almost all data from the electronic case report form (eCRF) will be listed. For example, time (mm:hh) will be excluded from almost all listings except for the PK and PD listings. From lab listings, the lab name and the original value for the dose in the units collected on the eCRF will be excluded and replaced with the value in SI units. Also a few variables collected on the AE eCRF and other eCRFs will be excluded from the listings.

Baseline will be defined as the last assessment completed prior to the administration of the study drug (Day 0, which corresponds with date of transplant).

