4.3 Methods for Handling Missing Data

No imputations will be made for missing data, except as described for the time-to-event analyses in Section 4.1 (above).

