8.1 Acute GVHD

For the primary and secondary endpoints as well as certain exploratory endpoints, Keystone criteria will be used for the determination of the severity of aGVHD. For outcomes at a defined time points, the event time will be defined as the time from the “start date” of first RGI-2001 infusion (i.e., transplant date/Day 0) to the first date aGVHD is diagnosed with Keystone criteria Grades II-IV. The first date of aGVHD will be identified using the following eCRFs:

- Initial report: *aGvHD_d* eCRFs with Question 10 = II-IV (i.e., Keystone Grades)
- Maximum report: *aGvHDmax* eCRFs with Question 1 = II-IV (i.e., Keystone Grades)

The first diagnosis date across the eCRFs meeting the above criteria will be used to define the “event time” for this analysis. Censoring: Subjects who are alive without these events will be censored at the date of completion of the last aGVHD assessment, with follow-up truncated at 180 days. Subjects who die without aGVHD will be treated as competing-risk events. The occurrence of aGVHD as a function of time will be calculated using cumulative-incidence estimates.

As an exploratory outcome, MAGIC criteria will be used for the determination of the severity of aGVHD. Event time will be defined as the time from the “start date” of first RGI-2001 infusion to the first date aGVHD is diagnosed with MAGIC criteria Grades II-IV. The first date will be identified using the following eCRFs:

- Initial report: *aGvHD_d* eCRFs with Question 8 = II-IV (i.e., MAGIC Grades)
- Maximum report: *aGvHDmax* eCRFs with any of the following three categories:
 - Grade II: Stage 3 skin and/or stage 1 liver and/or stage 1 upper GI and/or stage 1 lower GI (questions 3,4,5, and 6 on the eCRF)
 - Grade III: Stage 2-3 liver and/or stage 2-3 lower GI, with stage 0-3 skin and/or stage 0-1 upper GI
 - Grade IV: Stage 4 skin, liver, or lower GI involvement, with stage 0-1 upper GI

The first diagnosis date across the eCRFs meeting the above criteria will be used to define the “event time” for this analysis. Censoring and competing-risk considerations will be the same as with the Keystone criteria (above). The occurrence of aGVHD as a function of time will be calculated using cumulative-incidence estimates.

Similar to above, the analysis will be repeated for Keystone and Magic separately using only Grades III and IV.

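### SAP 8.8 summarises time to first systemic GvHD therapy by mean and median, in effect among users only, so the planned median cannot be read as delay; the companion proportion shows avoidance but reads low if follow-up is incomplete

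*SAP*

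**What the plan says.** SAP 8.8 takes the start date of the first relevant medication from the concomitant-medication form and leaves the list of medications to a table attachment that is not among the documents. It then plans two summaries. For timing: "This time analysis will be tabulated using continuous methods (mean/median/etc". For occurrence, the "number of patients with at least one of these medications will be calculated using a simple proportion of the safety population". It states no time origin, censoring rule, truncation or treatment of death.

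The SAP's general rules are these:

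- Section 4.1, time-to-event outcomes: "Point estimates of time-to-event outcomes will be obtained using either Kaplan-Meier or cumulative incidence estimates, depending on whether endpoints have competing risks". Section 8.0 repeats this for efficacy: "time-to-event outcomes with Kaplan-Meier estimates or cumulative incidence estimates for endpoints with competing risks".
- Section 4.1, continuous summaries: "Continuous variables will be summarized (based on the subjects with non-missing values".
- Section 4.3: "No imputations will be made for missing data, except as described for the time-to-event analyses in Section 4.1 (above". The exception in 4.1 deals only with incomplete or invalid dates.

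Other sections are fuller. For acute GvHD, section 8.1 has a censoring rule, a truncation point and this: "Subjects who die without aGVHD will be treated as competing-risk events". Section 9.3 (engraftment) describes times among those who engraft and adds a median read from the cumulative incidence curve.

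**The concern.** Time to first systemic therapy is a time-to-event outcome with three ways of having no event: never needing therapy, dying first, or leaving follow-up. A subject in any of these groups has no start date. With non-missing values only and no imputation, all of them drop out of the mean and median. Section 8.8 does not say that the summary covers users only, but this follows from 4.1 and 4.3.

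A reader of the study report would probably take a tabulated median time to systemic therapy as the time by which half the subjects had started. The planned figure is the middle start date among those who started within the observed period. In a study of GvHD prevention, that could be mistaken for evidence for or against delay.

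**Working it through.** There is no figure in 8.8 to reproduce, and the documents give no rates for systemic therapy, death or loss to follow-up. The rates below are assumptions, shown as ranges. From the documents come the planned number treated (50, SAP 2.3) and follow-up of up to one year (protocol 6.7), so T = 365 days.

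**Formulas.** Let a, d and w be constant, independent daily hazards of therapy, death and loss, and L = a + d + w. A one-year risk p, taken alone, gives a hazard of -ln(1 - p)/T.

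- Observed proportion starting therapy by T: (a/L)(1 - exp(-LT)). With w = 0 this equals the cumulative incidence.
- Mean among users: 1/L - T exp(-LT)/(1 - exp(-LT)).
- Median among users: -ln(1 - 0.5(1 - exp(-LT)))/L.

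**Base case: therapy risk 50% without death, death 15%, no loss.** aT = 0.6931, dT = 0.1625, LT = 0.8557, exp(-LT) = 0.425.

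- Cumulative incidence: (0.6931/0.8557) × 0.575 = 0.466.
- Mean among users: 426.6 - 365 × 0.425/0.575 = 156.8 days.
- Median among users: 426.6 × (-ln 0.7125) = 144.6 days.

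**Therapy hazard halved.** LT = 0.5091, exp(-LT) = 0.601. Cumulative incidence is 0.272, the users' mean 167.1 days and the users' median 159.5 days.

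For comparison, take the day on which the cumulative incidence curve reaches 20%. In the base case this is -ln(1 - 0.20/0.8101) × 426.6 = Day 121. With the hazard halved it is -ln(1 - 0.20/0.6808) × 717.0 = Day 249. The curve shows a shift of 128 days; the users-only median shows 15.

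**Range, with 15% death:**

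| One-year therapy risk without death | Users' mean, full → halved hazard | Cumulative incidence |
|---|---|---|
| 40% | 162 → 170 days | 37% → 21% |
| 50% | 157 → 167 days | 47% → 27% |
| 60% | 150 → 164 days | 56% → 34% |
| 70% | 142 → 160 days | 66% → 42% |

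**The users-only mean can mislead in direction.** Suppose 40% of subjects start early (mean Day 60) and 20% late (mean Day 242.5). The users' mean is (0.4 × 60 + 0.2 × 242.5)/0.6 = 121 days. Halving early starts gives (0.2 × 60 + 0.2 × 242.5)/0.4 = 151 days. Halving late starts gives (0.4 × 60 + 0.1 × 242.5)/0.5 = 97 days (96.5 before rounding). Both are benefits, yet the mean moves in opposite directions. If half of all users avoid therapy at random, it does not move at all.

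**It also moves without any change in therapy hazard.** With the base therapy hazard and one-year death of 5%, 15%, 30% or 45%, the users' mean is 160, 157, 151 or 144 days.

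**The simple proportion.** With complete follow-up it equals the cumulative incidence. Adding loss to the base case (true value 46.6%):

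| One-year loss | Crude proportion | Shortfall |
|---|---|---|
| 10% | 44.5% | 2.1 points |
| 20% | 42.4% | 4.2 points |
| 30% | 40.2% | 6.4 points |

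**The case against.** A reader might infer that the plan cannot show whether systemic therapy was avoided, or that it hides a treatment effect. The documents do not support that. The proportion planned in 8.8 has the full safety population as denominator, non-users included. If 60% of subjects were treated by one year under one scenario and 30% under another, with no death or loss, the users-only medians would be Day 142 and Day 166, but the proportion would read 60% and 30%. The halving would be plain. Only one of the two planned statistics is insensitive.

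A second tempting reading is that death biases the proportion. It does not, relative to a cumulative incidence with death as a competing event: death lowers both alike. Either figure has to be read beside mortality. The proportion's own weakness is loss to follow-up, and even the 6.4-point shortfall at 30% loss is below one standard error with 50 subjects: √(0.466 × 0.534/50) = 7.1 points.

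A third is that GRFS inherits the problem. Section 8.7 takes only a date: "Date of first use of systemic therapy for cGvHD will be defined using the *Concomitant Medication* eCRF", as described in 8.8. GRFS has its own censoring rule, counts death as an event and uses Kaplan-Meier.

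The stakes are also low. The outcome is not among the visible primary or secondary endpoints (the exploratory list is redacted). This SAP covers the RGI-2001 arm and plans no test of the outcome; the control comparison is in a separate SAP that was not supplied. Medication and outcome dates will be listed.

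All of this stands and limits the point. It does not answer the inconsistency with 4.1 and 8.0, or make the users-only median a measure of delay.

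**Conclusion.** The concern holds in a limited form. The timing summary in 8.8 is in effect restricted to users, has no censoring or competing-risk rule, conflicts with the SAP's general rule, and cannot be read as delay of therapy. In the illustrations, halving the therapy hazard moves the users' mean by about 8 to 17 days while cumulative incidence falls by 16 to 24 points. The companion proportion does show avoidance and reads low by about 2 to 6 points with 10% to 30% loss.

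These sizes rest on assumed constant, independent hazards and assumed rates. The users-only restriction is inferred from 4.1 and 4.3, and the unsupplied table attachment could state otherwise. This is a minor point about a descriptive endpoint and does not affect the primary or visible secondary analyses.

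**What to change.** Add to SAP 8.8 that time runs from the first RGI-2001 infusion to the first start of systemic GvHD therapy and is estimated by cumulative incidence. Treat death without prior systemic therapy as a competing event, censor at the last contact with medication data, and truncate at Day 365. Report estimates with confidence intervals at Days 100, 180 and 365.

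Keep the simple proportion of the safety population. Keep the mean and median, with a table label saying that they describe only subjects who started therapy. This mirrors what section 9.3 already does for engraftment.

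The cost is a short change of SAP wording, one more run of the cumulative incidence code needed for section 8.1, and slightly more reporting. No new data are needed.
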